encompassing both areas. The desired target temperatures for the equilibration phase (Rooms D and E above) are 60F and 80F (or 10F lesser than and 10F greater than the building's setpoint), while the desired target temperatures for the blinded temperature phase (Rooms A, B and C) are 68, 75.6 and 83.2F, if the building's target temperature is 68F, otherwise these should be offset with the difference. To obtain these temperatures, three rooms require heating and one room requires cooling. Each of the heated rooms will have a 1500W space heater and the cooled room will have a flexible temporary doorway installed with ductwork to a portable air conditioning unit. A wall-powered thermostat directed to switch by a rectified PID controller is then used to regulate the on/off cycle of each system. The building's airflow via the ductwork into the room may be damped with assistance from building maintenance. An air temperature logging system is set up in each room and in a preliminary study, is used to obtain the time constant and thermal stability of the room with the associated heating and cooling equipment. The key requirement for a suitable room is that the thermal stability must remain within 1C (1.8F) of a single value near the desired setpoint temperature for 10 minutes. Note, during both phases, it is unlikely these exact setpoints will be achieved at all times due to repeated opening and closing of doors, but fortunately this is not essential because ultimately the analysis is dependent on induced surface temperatures and the resulting induced core temperatures will be calculated for each subject based on the actual blinded temperature and the temperature of the room the IR thermometry is done within.

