The rooms will each consist of a portable tent with dimensions of at least 5x5ft base and height of 6ft. The critical requirement of said tent is sufficient thermal isolation from ambient temperatures to allow the maintenance of the required elevated or cooled temperature setpoints to within 1.8F. At present time, the most suitable tent is the THUNDERBAY Ice Cube 3 Man Portable Ice Shelter <https://www.amazon.com/gp/product/B019CU59VI>. This tent is surprisingly large, and has sufficient space to allow four adults to stand with 2 feet between adjacent people or two people with over 3 feet between them. The thermal radiant intensity of the walls of this tent do not match that of the elevated or cooled air temperature, because these walls directly contact and conduct to the ambient air and equilibrate between the ambient and internal temperatures, thus they radiate closer to the ambient temperature. Therefore, additional radiating membranes are used, consisting of sheets of fabric or paper hung from the ceiling or otherwise mounted with at least several inches displacement from the walls and having sufficient but low level of air flow to equilibrate the majority of the membrane to the internal air temperature. A GFCI-protected extension cord and powerstrip will be used to provide power to each tent.

The formula relied upon to obtain the ideal elevated temperatures is as follows, given as a lambda expression, which incorporates a first lambda (Python):

- $core2surf = \lambda core, air: core - (core-air)*0.191$

- $get_needed_room_air = \lambda air, febrile: core2surf(febrile, air) - ((98.6 - core2surf(febrile, air))/0.236)$

This gives us the needed heating temperature to get a desired change in body temperature, e.g. $get_needed_room_air(68, 100.4)$ returns 75.6F, meaning, in order to simulate a 100.4F core

temperature, a person must equilibrate to 75.6F air temperature before returning to receive a scan from the primary scanner located in 68F air temperature. This can be summarized more simply as, for every 1C (1.8F) elevation desired, the heated room must be that multiple of 4.23C (7.62F) above the scanning area's air temperature. Note, the exact coefficient was determined in a pilot study performed in June 2020, and may be refined by this study, which could alter the expected induced core temperatures.

Detailed Procedure - Blinded Temperature Study

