In a second analysis, the equilibration time constants will be evaluated for possible linear correlations with the demographic data, although it is possible the small sample size and variability will preclude the detection of any significant correlations. In case there are nonlinear relations, scatter plots will be examined to determine if a low-order polynomial or other reasonable fit could explain a relation, while keeping in mind the fact each additional test is a multiple comparison, thus increasing the required p-value multiplicatively. Scatter-plots, trends and r-values will be reported, and this data may be collated with future collections of independent datasets.

The controlled face temperature data will be analyzed for sensitivity and specificity of each non-contact system used, first in a blinded analysis and then in an open-label analysis. First, the blinded face temperature data will be used to assign each recorded datapoint into normal, mild and moderate and severe fever groups, corresponding to below 38C (100.4F), 38-39C (100.4-102.2F), 39-40C (102.2-104F) and above 40C (104F). Note, the heated rooms' air temperatures were selected to produce simulated core temperatures that straddle the mild and moderate thresholds (hence, a well-performing system should place 50% of the measurements above the threshold and 50% below while a system relying on a bias-to-normal method might place only 10% above the selected threshold), therefore the severe fevers group

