should likewise have few subjects placed within it. The sensitivity and specificity for assessing each of a mild and a moderate fever temperature will be assessed in a straightforward manner by revealing the labels and determining the fractions of correctly- and incorrectly-labelled datasets. These labels are generated by first matching the NFC UUID associated with an *nfc-temperature-scan* to the previous closest in time *nfc-room-scan* of this same NFC UUID and taking that room's air temperature difference to the temperature scanner's air temperature and converting to simulated core body temperature. Next, this now open-label data will be used to determine the mean and standard deviation across the core temperature scans of each of these four groups. The standard deviation of oral temperatures below the 38C threshold will be used to determine the false positive rate, using an assumed normal distribution or a low-dimensional parametric fit to the actual oral distribution. A parametric fit to the distribution above 38C will be used to determine the sensitivity and specificity for mild, moderate and severe fever thresholds, corresponding to 38-39C, 39-40C and 40C and above, respectively, using the sum of the area under the curve above the appropriate threshold. The linear correlation between oral and imaging temperatures in the below-threshold range will be tested for significance. A subset of the data consisting of equal parts of over-threshold (fevers, by oral temperatures) and under-threshold participants will be tested for significance, and this significance level compared with that of the whole set.

In a second analysis, the controlled face temperature data will be analyzed for effect of confounds with the primary non-contact thermographic system. In this case, the physiologic correction parameters obtained from each individual will be examined for linear correlates or nonlinear relationships with the demographic data. As with the equilibration data, scatter-plots, trends and r-values will be reported, and this data may be collated with future collections of independent datasets.

Quality control and data management

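### Both heated rooms target the fever cut-offs themselves, so moderate-fever sensitivity rests on scans at the band edge and understates an unbiased scanner

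*Combined protocol and SAP*

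**What the plan says.** - Controlled Temperature Rooms: the targets for Rooms A, B and C "are 68, 75.6 and 83.2F, if the building's target temperature is 68F". The surface model is "core - (core-air)*0.191". The worked example says the formula "returns 75.6F, meaning, in order to simulate a 100.4F core" temperature, and the short rule is that "the heated room must be that multiple of 4.23C (7.62F) above" the scanning area for each 1.8F of elevation wanted.
- Section D, Analyses: normal is below 100.4F, mild 100.4-102.2F, moderate 102.2-104F and severe above 104F. The heated rooms' "air temperatures were selected to produce simulated core temperatures that straddle the mild and moderate thresholds". A sound system is expected to split 50/50 at the threshold, and a bias-to-normal system might put only 10% above.
- Section D then obtains sensitivity and specificity for mild and for moderate fever by revealing the labels and "determining the fractions of correctly- and incorrectly-labelled datasets". A label comes from the air-temperature difference between room and scanner, converted to simulated core.
- Controlled Temperature Rooms also says that exact setpoints will probably not hold, and that induced temperatures will be calculated for each subject from actual air temperatures.

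**The concern.** A 50/50 split at a cut-off is a useful calibration check, and it is what an unbiased device should show. It is not sensitivity. When the true value sits on the cut-off, whether a scan is labelled above or below depends on small departures from target, and a device with ordinary error will often disagree with the label. The plan takes both quantities from the same scans.

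The harm is concentrated in moderate fever. Room C is the only room near that band and it targets the lower edge. The Introduction names sensitivity and specificity by fever group as an aim, with regulatory use in view. A sound scanner could therefore be published with a low moderate-fever sensitivity that reflects where the room was placed, not how the scanner performed.

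**Working it through.** **Reproducing the setpoints.** With scanner air at 68F, surface temperature is s = core - 0.191 x (core - 68), and room air is s - (98.6 - s)/0.236.
- 98.6F: s = 92.755, room 67.99F
- 100.4F: s = 94.212, room 75.617F
- 102.2F: s = 95.668, room 83.243F

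These round to the printed 68, 75.6 and 83.2F, so Rooms B and C target the two cut-offs. Inverting the printed values (4.237F of air per 1F of core) gives 100.396F and 102.190F, which are 0.004F and 0.010F below the cut-offs.

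**Inputs for an unbiased scanner.**
- Error SD 0.48F: the upper bound on physiologic variability in Population Size.
- Drift: within 1.8F of air, so 1.8 x 0.236 = 0.42F of simulated core. A uniform shape is assumed (SD 0.42/√3 = 0.245F), centred on the cut-offs.
- Mean core 98.6F, the formula's baseline. Core SD is 0 (fixed), 1F (Introduction) or 0.6F (an assumed lower value). Equal scans per room.

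**Air-only labels.** Half of Room C is labelled moderate, by 0 to 0.42F. Agreement is the average of Φ(x/σ) over that range, which is [uΦ(u) + φ(u) - φ(0)]/u with u = 0.425/σ.
- Core fixed, σ = 0.48: u = 0.885, giving (0.719 + 0.270 - 0.399)/0.885 = 0.67.
- Core SD 1F, σ = √(0.48² + 1²) = 1.11: u = 0.383, giving 0.575.

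The other indices dilute the edge room with rooms far from the cut-off. With core fixed:
- 38C sensitivity = (1 + 0.5 x 0.67)/1.5 = 0.89, and 38C specificity is the same by symmetry.
- 39C specificity = (2 + 0.5 x 0.67)/2.5 = 0.93.

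**Own-core labels.** Label and scan are correlated with ρ = τ/√(τ² + 0.48²), where τ² = core SD² + 0.245². Room C agreement above the cut-off is 1/2 + arcsin(ρ)/π.
- Core SD 0.6F: ρ = 0.804, giving 0.80.
- Core SD 1F: ρ = 0.906, giving 0.86, or 0.85 once the few Room B scans labelled above 102.2F are counted.

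Simulation with one million scans per room agrees:

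| Labels | Core SD | 38C sens. | 38C spec. | 39C sens. | 39C spec. |
|---|---|---|---|---|---|
| Air only | 0 | 89% | 89% | 67% | 93% |
| Air only | 1F | 82% | 82% | 57.5% | 89% |
| Own core | 0.6F | 92% | 92% | 80% | 96% |
| Own core | 1F | 93% | 93% | 85% | 96% |

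**The same scanner away from the edge.** Room C is 1.8F above 38C and Room A 1.8F below. Total SD is √(0.48² + 0.245²) = 0.54F with core fixed, or 1.14F with core SD 1F. Φ(1.8/0.54) is about 100% and Φ(1.8/1.14) about 94%, for both indices. At mean core 97.9F (the low average in the Introduction) Room C's margin is 1.1F, so its sensitivity is 98% to 83%.

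**Why the edge fractions must stay.** Take a scanner that shrinks values 30% towards 98.6F, core fixed, with SD √(0.48² + (0.7 x 0.245)²) = 0.51F.
- Room C reads 98.6 + 0.7 x 3.6 = 101.12F, so 38C sensitivity is still Φ(0.72/0.51) = 92%.
- Room B reads 99.86F, so its fraction above 38C drops from 50% to Φ(-0.54/0.51) = 14-15%.
- Room C's fraction above 39C drops from 50% to Φ(-1.08/0.51) = 2%.

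The expected fraction is not always 50%. At mean core 97.9F with core fixed, an unbiased scanner puts only Φ(-0.7/0.54) = 10% of Room B above 38C, the figure the plan associates with a biased device.

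**The case against.** The placement is deliberate and explained: it is meant to expose bias-to-normal, and the shrinkage example shows that it can. That stands. The fault lies only in also scoring those scans as correct or incorrect.

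A reader might infer that no scan will be labelled moderate, since at the exact printed setpoints Room C falls just below 102.2F. The documents do not support this. The miss is 0.010F of core (0.043F of air) and comes from rounding. The protocol expects setpoints to vary and calculates from actual air temperatures. With uniform drift of 0.5 to 1.8F around the printed setpoints, about 46-49% of Room C scans become moderate.

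A reader might also infer that every accuracy figure will be poor. That is not so: only 39C sensitivity is badly affected, because rooms away from the cut-off support the other three.

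The label rule is open to two readings. Section D mentions only the air difference, but Population Size says temperatures are referenced to each individual's core, and an oral reading follows each set of scans. On that reading moderate sensitivity is 80-85%, so the lower range cannot be presented as the only answer.

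Section D also plans group means and a parametric area-above-threshold estimate. Neither adds exposure inside the moderate band.

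**Conclusion.** The point holds, mainly for moderate-fever sensitivity. Both heated rooms target cut-offs, no room targets the inside of the moderate band, and correct-label scoring there gives an unbiased scanner about 57-67% under air-only labels or about 80-85% under own-core labels. Sensitivity and specificity at 38C (82-93%) and specificity at 39C (89-96%) are reduced less.

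The figures assume 0.48F error, uniform drift within 1.8F of air, equal scans per room and mean core 98.6F. With a lower mean core and air-only labels, moderate sensitivity would be lower still, because the label keeps the 98.6F baseline while the scanner reads the true, lower value. The straddling design is not itself an error, and the rounding of the setpoints is a detail. I would class this as should-fix: it changes what can be concluded about moderate fever, and the remedy is mostly in the analysis text.

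**What to change.** Keep the rooms and amend Section D:

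1. Report sensitivity and specificity at 38C from Room C scans (positives) and Room A scans (negatives). Note that Room C sensitivity depends on mean core: about 94-100% at 98.6F and about 83-98% at 97.9F for the scanner modelled here.
2. For Room B at 38C and Room C at 39C, report the observed fraction above the cut-off against the fraction expected from the actual air temperatures and the participants' oral temperatures. Present this as the bias-to-normal check and do not call it sensitivity. It must accompany item 1, because the Room A and C table alone can miss moderate shrinkage.
3. Make no claim about moderate-fever sensitivity unless the simulated target is moved off the band edge. Align the aim in the Introduction with this.

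State also whether labels use the air difference alone or each person's own core.

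Excluding scans within the method's stated 0.25C (0.45F) of a cut-off is not a workable alternative. Drift moves simulated core by at most 0.42F, so with air-only labels the rule removes every Room B and Room C scan. With own-core labels it removes 42-53% of each.

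The cost is new wording and a re-tabulation. Room B, a third of the blinded-phase scans, leaves the sensitivity and specificity table, and there is no direct estimate of moderate-fever sensitivity.

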The number of samples required to understand the impact of environmental or physiological confounds on surface temperature is dependent on the variability in the core-to-surface temperature physiologic offset. The variability in core body temperature has been found to be close to 1F but note the research design proposed here is not dependent on normal person-to-person variability in core temperature because the temperatures obtained are all referenced to each individual's core temperature. To estimate the likely physiologic variability in the population, we can extrapolate based on surface temperature data taken by the primary thermographic system obtained over the past six months because this should be approximately the vector sum of variability in core temperature, measurement accuracy, and the physiologic variability. This data must be interpreted with caution, because these have been obtained with less control over environmental conditions and furthermore we do not know the core body temperature variability in the preliminary data population, but it can provide a reasonable error bound. This data shows a standard deviation of 1.11F (note, this value is obtained without *any* bias-to-normal algorithm, which appears to be a novel feature in this research), which would suggest the physiologic variability component is at most 0.48F, or half a degree. Therefore, in order to determine the sensitivity and specificity at detecting elevated temperatures of 1.8F (100.4F threshold) to within 20% (meaning, can we significantly distinguish 100.40 from 100.04F with the aforementioned standard deviation in a one-sided paired t-test), we require 28 participants. To account for possible data collection failures, we intend to recruit as many as 45 participants.

Data Collection

- Demographic and clinical data: minimal demographic and clinical data will be collected by interview with the participant at the time of the imaging studies including age, gender, any disease- or autonomic-modulating treatment, height, weight and any antipyretic medications in past 12 hours in order to allow adjustment for confounding factors. We do not intend to collect data on menstrual cycle due to the additional potential privacy concerns this will place on participants worried about this data which is significantly more sensitive than other data being collected.

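### The rule that labels each scan for sensitivity and specificity uses two air temperatures and names no core baseline, so the reference standard is undefined; a fixed baseline would mis-score an accurate device

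*Combined protocol and SAP*

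**What the plan says.** **Label rule.** Section D (Analyses) matches each temperature scan to the same participant's preceding room scan and forms the label by "taking that room's air temperature difference to the temperature scanner's air temperature and converting to simulated core body temperature". Sensitivity and specificity are then the fractions of scans that agree or disagree with the label. Controlled Temperature Rooms gives a second version of the rule: induced core temperatures are "calculated for each subject based on the actual blinded temperature and the temperature of the room the IR thermometry is done within". Both versions take two air temperatures and nothing else.

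**Conversion.** Controlled Temperature Rooms summarises the model as a rise: "for every 1C (1.8F) elevation desired, the heated room must be that multiple of 4.23C (7.62F) above the scanning area's air temperature". The function used to choose room temperatures has 98.6 hard-coded: "core2surf(febrile, air) - ((98.6 - core2surf(febrile, air))/0.236". The blinded-phase targets "are 68, 75.6 and 83.2F, if the building's target temperature is 68F".

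**Individual baseline.** Population Size says that "the temperatures obtained are all referenced to each individual's core temperature". On that ground it removes core variability from the observed SD of 1.11F, "which would suggest the physiologic variability component is at most 0.48F, or half a degree".

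**Expected result.** Section D says the heated rooms were chosen so that simulated temperatures straddle the mild and moderate thresholds, and that a good system should put half of its readings on each side.

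**Oral readings.** One is taken after every set of scans (Oral Thermometry; Detailed Procedure - Blinded Temperature Study). Section D uses them for a false positive rate, a correlation and an oral-fever subset, but not for the label.

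**The concern.** A rise cannot be classified at 38, 39 or 40C until it is added to a baseline. Two analysts could follow Section D faithfully, one adding the rise to 98.6F and the other to the participant's own oral temperature, and report materially different sensitivities for the same device.

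If the baseline is fixed, the label ignores the person's own core temperature while an accurate device responds to it. Normal variation between people is then counted as device error. The label match is the first accuracy estimate for every system tested. The protocol also criticises earlier studies for settling a threshold after seeing the data, so the rule should be settled before the labels are revealed.

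**Working it through.** **1. The plan's own figures.** Running the printed functions with 68F scanner air gives 75.62F for a 100.4F target and 83.24F for 102.2F, matching the stated 75.6 and 83.2F. Also √(1.11² − 1²) = 0.48F, so the Population Size figure is reproduced by removing a 1F core SD.

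**2. What the air difference determines.** Let b be a person's core, R the room air and S the scanner air.
- Surface temperature after equilibration = b − 0.191(b − R).
- Simulated core = (surface − 0.191 S)/0.809 = b + (0.191/0.809)(R − S) = b + 0.236(R − S).

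The baseline enters one for one. In a 75.6F room with 68F scanner air, the model gives 99.69F for a person at 97.9F, 100.39F at 98.6F and 101.39F at 99.6F. A fixed 98.6F baseline labels all three 100.39F.

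**3. A check that needs no assumed SD.** With any fixed baseline and steady air, every Room B scan has the same label. Section D expects a good system to place half its readings above the threshold and half below. Whichever class Room B receives, half of those readings disagree with it.

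**4. Labels at the printed setpoints, 98.6F baseline.**
- Room B: 98.6 + 0.236 × 7.6 = 100.394F, below 100.4F.
- Room C: 98.6 + 0.236 × 15.2 = 102.187F, below 102.2F.

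The air difference falls short of the cut-offs by 1.8/0.236 − 7.6 = 0.03F and 3.6/0.236 − 15.2 = 0.05F. The room requirement is that "the thermal stability must remain within 1C (1.8F) of a single value near the desired setpoint temperature for 10 minutes", so the tolerated drift is far larger than the margin that decides the class.

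**5. Score of an error-free device against a fixed 98.6F label.** Inputs from the documents: core SD about 1F and mean 97.9 to 98.6F (Introduction). Assumptions: normal core temperature, equal numbers in Rooms A, B and C, nominal rises of 0, 1.8 and 3.6F, and uniform air drift in B and C. Simulated sensitivity/specificity:

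| Drift | Mean core | 100.4F | 102.2F |
|---|---|---|---|
| ±1.8F | 98.6F | 83%/84% | 58%/90% |
| ±1.8F | 97.9F | 68%/94% | 31%/96% |
| ±0.9F | 98.6F | 82%/82% | 54%/89% |
| ±0.9F | 97.9F | 67%/92.5% | 28%/96% |
| ±3.6F | 98.6F | 85%/86% | 66%/91% |
| ±3.6F | 97.9F | 69%/95% | 39%/97% |

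With ±1.8F drift, 42–43% of Room B readings disagree with the label at 100.4F. With core SD 0.7F instead of 1F, the ±1.8F rows become 87%/87% to 70%/97% at 100.4F and 62%/92% to 25%/98% at 102.2F.

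**6. Zero drift, mean core 98.6F.** The chances of an error-free reading above 100.4F in Rooms A, B and C are 0.036, 0.500 and 0.964.
- Room B labelled positive: sensitivity (0.500 + 0.964)/2 = 73%, specificity 1 − 0.036 = 96%.
- Room B labelled negative, as at the printed setpoints: sensitivity 96%, specificity 1 − (0.036 + 0.500)/2 = 73%. No label is then positive at 102.2F, so sensitivity there cannot be computed.

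**7. Own-oral label, ±1.8F drift, error-free device.** Sensitivity across the two means is 90–93% at 100.4F and 72–82% at 102.2F with an assumed oral-error SD of 0.5F. With 0.18F (the 0.1C thermometer accuracy in the Introduction, treated as an SD) it is about 97% and 90–94%.

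**The case against.** The strongest reply is that this is an omission. Nowhere do the documents say that labels use 98.6F; that figure sits in a formula for choosing room temperatures. Population Size, the per-subject wording in Controlled Temperature Rooms and the 50/50 expectation all fit an own-core baseline. A supplement on evaluation methods and a Study Schema are mentioned but were not available, and the formula could be there. All this stands as evidence of possible intent. It does not put an own-core term into the rule, which is stated twice with the same two air temperatures.

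Section D also derives a false positive rate from the oral SD and later estimates from parametric fits, so core variation does enter elsewhere. That is correct. The figures here cover the label match only.

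Two stronger readings are tempting, and the documents do not support them.
- **A reader might infer that a fixed label ranks bias-to-normal devices above accurate ones.** That needs a device able to separate own core from the induced rise, while skin temperature carries only their sum. Shrinking the whole reading toward 98.6F still scores worse under the fixed label: at mean core 98.6F and ±1.8F drift, retaining half of the deviation cuts sensitivity at 100.4F from 83% to 35%.
- **A reader might infer that the 28 participants rest on too small a variance,** because a fixed baseline would leave the 1F core SD in. That number comes from a paired t-test. If the pairing is within participant, own core cancels whatever baseline the label uses.

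**Conclusion.** The concern holds as an undefined reference standard that conflicts, as written, with the Population Size statement. It needs correcting before labels are revealed, because following the written rule with any fixed baseline mis-scores an accurate device. The Room B argument shows this without an assumed core SD; it needs only steady air and the plan's own 50/50 expectation.

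The percentages are conditional on 98.6F being the baseline and on the core distribution, room balance and drift stated above. The lowest sensitivities also need a mean core of 97.9F. With little or no drift, the error moves between sensitivity and specificity according to which side of the cut-off the room falls. It is not established that the investigators intend a fixed baseline. No conclusion is drawn here about device ranking or the adequacy of 28 participants.

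**What to change.** In Section D, define the label for each room visit as:

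label = participant's own oral temperature from that visit + 0.236 (or the re-estimated coefficient) × (room air − scanner air),

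classified at 38, 39 and 40C. Then:
- replace the fixed 50% expectation with the observed share of labels above each threshold;
- as a sensitivity analysis, use the mean of the participant's three blinded-phase oral readings as baseline, noting that room-related oral error may be shared across them;
- reconcile the label wording in Controlled Temperature Rooms and Section D, and the role of 98.6F in the setpoint formula, with Population Size.

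The cost is analysis wording and code, since the oral readings are already taken after each visit. The drawback is that oral error enters the label, and the Introduction lists probe placement, speaking and air temperature among its sources. Even an error-free device would then fall short of 100%, by the amounts in step 7 of the working, so the report should state the oral error assumed.

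### The planned SD of raw scans by fever group mixes true temperature spread with scanner error, so a scanner that compresses readings toward normal shows the smaller SD

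*Combined protocol and SAP*

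**What the plan says.** All references are to the Combined protocol and SAP.

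- **D. Analyses, open-label step.** Once the labels are revealed, the data are used to "determine the mean and standard deviation across the core temperature scans of each of these four groups". The sentence does not split by room or subtract a reference value. It also does not say whether the groups come from the room label, from the room label plus the participant's own core temperature, or from the scanner's reading.
- **D. Analyses, group definition.** Normal, mild, moderate and severe are set by fixed cuts, "corresponding to below 38C (100.4F), 38-39C (100.4-102.2F), 39-40C (102.2-104F) and above 40C (104F". The heated rooms were chosen to "produce simulated core temperatures that straddle the mild and moderate thresholds", so that "a well-performing system should place 50% of the measurements above the threshold and 50% below".
- **Controlled Temperature Rooms.** The target air temperatures are given as "Rooms A, B and C) are 68, 75.6 and 83.2F". The formula for a 100.4F target "returns 75.6F, meaning, in order to simulate a 100.4F core" temperature when the scan is taken at 68F. The shorthand rule is "for every 1C (1.8F) elevation desired, the heated room must be that multiple of 4.23C (7.62F) above" the scanning area.
- **Individual referencing.** Population Size says temperatures are referenced to each person's core. Controlled Temperature Rooms says induced core temperatures are calculated for each subject from the actual air temperatures. The sentence on mean and SD carries over neither statement.

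**The concern.** A main purpose of the study, set out in A. Introduction, is to expose devices that pull readings toward normal. The same section warns that a strong correlation can coexist with such compression. A raw SD by fever group has a similar weakness. It rises when a scanner correctly follows real differences between people and rooms, and falls when a scanner suppresses them.

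A reader given one mean and one SD per system and group will naturally take the SD as precision, and on that reading the compressed device looks better. The mean beside it is hard to interpret unless the room mix in the group is known. Even an unbiased scanner has a normal-group mean of about 99.1 to 99.2F, because that group includes about half of Room B.

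**Working it through.** **Inputs.** Core SD about 1F, scan SD 1.11F and physiologic SD at most 0.48F (Population Size). Room air 68, 75.6 and 83.2F, and 7.62F of air per 1.8F of core (Controlled Temperature Rooms). Cuts at 100.4, 102.2 and 104F (D. Analyses).

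**Assumptions.** Mean core 98.6F, equal use of the three rooms, and linear compression: reading = 98.6 + k × (uncompressed reading − 98.6).

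**1. Reproduce the plan's figures.** The protocol's formula at 68F gives 67.99, 75.62 and 83.24F of air for cores of 98.6, 100.4 and 102.2F. Rooms A, B and C are therefore 1.8F apart in simulated core, and B and C sit on the first two cuts. √(1.11² − 1²) = 0.48F matches the stated physiologic component.

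**2. Values of k.** Two come from the protocol.
- Outputs of 97–99F for inputs of 95–103F (A. Introduction) give k = 2/8 = 0.25.
- Only 10% of Room B above threshold (D. Analyses) gives 1.8(1 − k) = 1.2816 × 1.11k, so k = 1.8/3.2226 = 0.56.

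k = 0.30 is added as an illustration.

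**3. Groups by room label.** Normal is 2/3 Room A and 1/3 Room B; mild is half B and half C; moderate is Room C only. Between-room SD is 1.8 × √(2/9) = 0.85F for normal and 0.90F for mild. Group SD = k × √(1.11² + between²). Mild mean = 98.6 + k × 2.7.

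| k | SD, one room | SD, normal | SD, mild | Mean, mild |
|---|---|---|---|---|
| 1 (unbiased) | 1.11 | 1.40 | 1.43 | 101.3 |
| 0.56 | 0.62 | 0.78 | 0.80 | 100.1 |
| 0.30 | 0.33 | 0.42 | 0.43 | 99.4 |
| 0.25 | 0.28 | 0.35 | 0.36 | 99.3 |

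Letting room air drift by ±1.8F, so that drift decides the labels, lowers the unbiased SDs to 1.34F and 1.31F. The ordering is unchanged.

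**4. Groups by room label plus own core (simulation).** Unbiased SDs are 1.09, 0.70 and 0.67F in normal, mild and moderate. At k = 0.56 they are 0.61, 0.39 and 0.38F; at k = 0.25, 0.27, 0.18 and 0.17F. The cuts truncate the spread, but the ordering is the same. It also holds at a mean core of 97.9F (unbiased 1.24, 0.70 and 0.64F; k = 0.25 gives 0.31, 0.17 and 0.16F).

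**5. Groups by the scanner's own reading (simulation).** Unbiased SDs are 0.51F in mild and 0.48F in moderate. A uniform spread over a 1.8F band has SD 1.8/√12 = 0.52F, so these figures mostly describe the band.

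**6. Error against the participant's own simulated core.** Mean error = (k − 1) × rise, with rises of 0, 1.8 and 3.6F. Error SD = √((1 − k)² × 1² + (k × 0.48)²).

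| k | Mean error, A / B / C | Error SD |
|---|---|---|
| 1 | 0 / 0 / 0 | 0.48 |
| 0.56 | 0 / −0.79 / −1.58 | 0.52 |
| 0.30 | 0 / −1.26 / −2.52 | 0.71 |
| 0.25 | 0 / −1.35 / −2.70 | 0.76 |

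Room drift adds at most about 0.02F to these SDs. The unbiased scanner has the smallest error SD, and the smallest mean error in the heated rooms.

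**7. Room-only reference.** If the reference omits the participant's own core, the error SD is 1.11F unbiased against 0.37 to 0.59F at k = 0.30, depending on whether noise is compressed too. The wrong ordering remains. With own core included it is 0.48F against 0.73 to 0.87F (drift included).

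**The case against.** The strongest defence is that the SD is a descriptive line. The plan never calls it precision and never ranks systems on it. Its stated test for compression is the share of readings above a threshold, 50% for a good system against perhaps 10%, and sensitivity and specificity follow from that. This stands, and it limits the point to how one summary will be read.

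A reader might infer four stronger things that the documents do not support:

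- **That this is the only continuous summary planned.** D. Analyses also plans the oral-to-imaging correlation, a balanced-subset comparison and parametric fits. None of them is scan error against simulated core.
- **That the summary says nothing about bias.** With label-based groups the mean does: about 101.3F against 99.4F in mild at k = 0.30. Interpreting it needs the room mix, which shifts with the population. With own-core labels, normal is 64/33/3% Rooms A/B/C at a mean core of 98.6F and 53/40/8% at 97.9F.
- **That room mixing alone causes the reversal.** For raw scans it does not, since compression shrinks the SD within a single room too (1.11F against 0.62F or 0.28F). Mixing itself reverses the ordering only if scans are first referenced to own oral temperature. The unbiased SD then goes from 0.48F in one room to 0.97F (normal) and 1.02F (mild), while k = 0.56 goes from 0.52F to 0.70–0.72F.
- **That all four groups mix rooms.** Moderate is 92 to 100% Room C at a mean core of 98.6F, and the plan expects few subjects in severe.

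**Conclusion.** The concern holds in a limited form. The raw SD by fever group confounds true spread in simulated core with scanner error. With label-based groups, at the protocol's own variance figures, the unbiased scanner's SD is about 1.8 times that of a scanner with k = 0.56 (1/0.56) and 4 times that of one with k = 0.25 (1/0.25). With groups formed by the scanner's reading, the mild and moderate SDs mostly reflect the 1.8F band width.

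The direction rests on linear compression toward 98.6F and on core variation of about 1F. The exact sizes depend on mean core, room use and how the groups are formed, which the plan leaves open. The sensitivity and specificity analysis is unaffected. The change should be made because the present summary can favour the fault the study sets out to find, and no other planned summary gives error against simulated core.

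**What to change.** In D. Analyses:

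1. State how the four groups are formed.
2. For each system, average the repeat scans within a visit. Then compute reading minus the participant's simulated core for that visit, defined as the participant's own oral temperature plus the rise implied by the actual room-to-scanner air difference. This agrees with the individual referencing in Population Size and Controlled Temperature Rooms.
3. Report the mean and SD of this error by Room A, B and C, with participant as the unit, as the main continuous summary.
4. Keep the raw fever-group mean and SD as descriptive only, without reading the SD as precision.

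The cost is a few sentences and one table. Oral temperature is already taken after each set of scans, and air temperatures are logged. The small downside is that oral measurement error enters the error SD. If it is independent with SD s, the unbiased figure becomes √(0.48² + s²). As an illustration, taking s = 0.18F (the 0.1C oral thermometer accuracy in A. Introduction, treated as an SD by assumption) gives 0.51F. The same variance is added for every system, so the ordering does not change.
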